5.1 Research question

1. What is the impact of differing completion rates of DSME programmes on ability to self-care (primary outcome), diabetes distress and health related quality of life in type 2 diabetes.

5.2 Outcome

The primary outcome measure will be measured as:

- Change in self-care activities outcome measure (pre and post intervention) using the Diabetes Self-Management Questionnaire - Revised (DSMQ-R) scale (48).

Secondary outcome data will capture data on:

- Change in diabetes distress (pre and post intervention) using the Problem Areas in Diabetes (PAID) tool (49).
- Quality of life outcome measures (pre and post intervention) using the PROMIS-Global Health V1.2 scale (50).

Other preliminary data will explore whether deprivation and diabetes duration have any impact on PROMs across the four groups.

STUDY DESIGN AND METHODS OF DATA COLLECTION

This is a quantitative feasibility study focusing on the impact of differing completion rates of DSME programmes on psychometric outcomes pre and 4 months post intervention.

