Original contribution to knowledge: Whilst the current literature evidences the clear benefits for people with type 2 diabetes attending DSME programmes, there is minimal understanding of the benefits of partial DSME completion on a person's ability to self-care despite national consensus accepting 60% attendance as 'completed'. The proposed research aims to test the feasibility of conducting a full randomised control trial to evaluate the effectiveness of DSME programmes on psychometric outcomes with differing completion rates.

Lay Summary

Type 2 diabetes accounts for 90% of all diabetes diagnoses. Without proper care, type 2 diabetes can result in complications such as stroke, heart disease, kidney disease, eye disease and nerve damage. On average, a person with diabetes spends less than three hours a year with a healthcare professional meaning patients must manage their own diabetes almost 100% of the time. Diabetes self-management education plays an important role in helping people stay healthy, live well, and avoid life threatening complications and is proven to be effective in lowering blood glucose levels and preventing health problems later in life. Despite an increased awareness of the importance of education for people with type 2 diabetes, attendance at education programmes remains very poor with little to no change over the past decade.

Many things can prevent attendance or completion of education programmes, including physical and mental health issues, reduced finances, work and childcare commitments, location of education programmes and lack of information on programme content or availability. Little is known on the effectiveness of only attending part of an education programme on a person's ability to self-care.

This study will examine the impact of differing completion rates of diabetes self-management education programmes on a person's self-care skills. The psychological impact of not completing a diabetes self-management education programme is unknown and a better understanding of this could help tailor future education offers for people with type 2 diabetes. This is a smaller study to see if a larger project is feasible in the future.

Funding and Support in Kind

FUNDER(S)	FINANCIAL AND NON-FINANCIAL SUPPORT GIVEN

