Internationally the benchmark for recording a patient as completed DSME is attendance at $\geq 60\%$ of a programme's content (23,41–43), a discord with the literature measuring effectiveness of landmark studies at 100% completion (25,39). A record of DSME attendance is given for patients who sign up and engage with $>10\%$ of materials (23,41,43).

There is no research available measuring the impact of non-completion on UK DSME programme effectiveness or internationally on the impact of differing completion rates on patient reported outcome measures (PROMs) despite the acceptance of completion ($\geq 60\%$) at discord with legendary studies benchmarking completed at 100%. The aims of this study are to explore if patients who attend minimal aspects (10%) of DSME programmes gain clinically significant improvements in ability to self-care compared to those who do not attend, and if the nationally accepted 60 % completion rate is as effective as 100% completion.

THEORETICAL FRAMEWORK

Philosophical assumptions (also referred to as epistemology) influence our views about how phenomena should be approached (44) assisting researchers in refining the types of evidence required, how it should be collected, and how it should be interpreted. This quantitative study will adopt an experimental hypothesis driven design whereby the variable or intervention is controlled, with the exception of a control group, to attempt to establish causal effect of an intervention, in this case DSME completion rates. Whilst the most powerful and highly regarded form of experimental study remains the randomised control trial (RCT), this study will test the feasibility of conducting a full RCT.

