4.1 Null hypothesis

Differing DSME completion rates have no impact on a person's ability to self-care, diabetes distress or health related quality of life.

RESEARCH QUESTION

Using a quantitative approach this feasibility study aims to explore if patients who attend minimal aspects (10%) of DSME programmes gain clinically significant improvements in ability to self-care compared to those who do not attend, and if the nationally accepted 60 % completion rate is as effective as 100% completion on patient reported outcome measures.

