6.1 Design

This is a single-centre randomised feasibility study evaluating the impact of different completion rates of DSME programmes on psychometric outcomes specifically looking at ability to self-care, diabetes distress and quality of life. DSME will be the intervention and will typically be delivered within 3 weeks of the baseline appointment. There is a deliberate short separation between education intervention and follow up psychometric tests of 3-4 months to allow participants the opportunity to adopt any behaviour changes following the DSME programme whilst minimising the risk of not receiving the full NICE recommended DSME programme and to broadly align with landmark studies. Landmark studies namely DCCT (26,27) and DESMOND (25) evidenced a statistically

significant improvement to PROMs at 4 months post education intervention, however HbA_{1c} changes were not significant within this timeframe despite being statistically powered. A recent systematic review (38) concluded that as DSME is primarily focused on behavioural change to facilitate glycaemic control, efficacy measures should focus on behavioural and psychosocial changes, however these are often overlooked. This study is a feasibility trial and by its very nature is not statistically powered, therefore despite HbA_{1c} being arguably the measure of choice within the literature for measuring effectiveness of diabetes interventions, this study will use PROMs as its primary outcome measure.

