6.4 Data Analysis

Descriptive analysis will be completed for all demographic data presenting continuous variables as means \pm standard deviation and categorical variables as numbers (%). Data will be tested for normality using a Shapiro-Wilk test and subject to visual inspection of histograms and normal Q-Q plots.

Psychometric outcomes will include the Diabetes Self-Management Questionnaire-Revised (DSMQ-R)(48), Problem Areas in Diabetes (PAID) scale (49) and the Patient reported outcome measures information system (PROMIS) Global Health scale v1.2 (50). Data will be treated as continuous and analysis of the difference in the mean before and after intervention will be conducted using an analysis of variance (ANOVA) test to check for statistical and clinical difference in the mean across the four groups.

Statistical analysis will be conducted using IBM® SPSS® Premium 29 with support from University of Liverpool statisticians. The alpha level will be set at 5% for statistical significance.

Whilst a statistically significant difference is desirable, it is important to understand what would represent a meaningful clinical change for a patient. As such the minimal clinically important difference (MCID) will be reported to measure the smallest difference in which the patient would perceive a benefit (61–64). Where the MCID is not published this will be calculated using a distribution-based derivation using 0.5 SD of the observed change in PROM score (62,65). Whilst this approach is not without its limitations (61,63) no consensus on the ideal means of determining the MCID is available (63). A systematic review concluded that 0.5 SD of the observed change approximated the published MCID in the majority of cases popularising this derivation in the literature (65).

MCID will be classed as >2 T-score points for the PROMIS Global Health v1.2 (66) in which physical health and mental health are given separate T-scores with a 95% confidence interval. The MCID will be calculated for PAID and DSMQ-R.

Recruitment of participants and the number of dropouts will be reported descriptively (frequencies and percentages). Due to the aims of this study considering differing completion levels of DSME, intention to treat analysis will not be used. Where participants allocated to a group do not fully complete the required amount of DSME there results would be withdrawn from the final analysis.

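### Section 5.2 gives outcome status only to the questionnaire effects, not to the feasibility measures, and the effect tests cannot support a finding that 60% attendance works as well as 100%

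*Combined protocol and SAP*

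**What the plan says.** **Feasibility purpose.** The abstract (original contribution to knowledge) says: "The proposed research aims to test the feasibility of conducting a full randomised control trial to evaluate the effectiveness of DSME programmes". The Theoretical Framework section repeats that "this study will test the feasibility of conducting a full RCT".

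**Effect purpose.** The Research Question section says that "this feasibility study aims to explore if patients who attend minimal aspects (10%) of DSME programmes gain clinically significant improvements in ability to self-care" compared with non-attenders, and goes on to ask whether 60% completion is as effective as 100%. Section 5.1 asks: "What is the impact of differing completion rates of DSME programmes on ability to self-care (primary outcome), diabetes distress and health related quality of life". The Study Summary, the abstract's aim, the rationale and Section 6.1 are worded in the same direction, and the null hypothesis in 4.1 concerns effect only.

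**Outcomes.** Section 5.2 names as primary "Change in self-care activities outcome measure (pre and post intervention) using the Diabetes Self-Management Questionnaire - Revised (DSMQ-R) scale". PAID and PROMIS Global Health are secondary, followed by exploratory work on deprivation and diabetes duration. No feasibility measure is listed.

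**Analysis.** Section 6.1 states: "This study is a feasibility trial and by its very nature is not statistically powered". Section 6.4 compares mean change across the four groups by ANOVA and adds: "The alpha level will be set at 5% for statistical significance". It also reports a minimal clinically important difference (MCID), derived for DSMQ-R and PAID as half the SD of observed change. No equivalence or non-inferiority margin is given.

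**Where feasibility does appear.** The abstract promises eligibility, recruitment and retention rates. Section 6.4 reports recruitment and dropout descriptively. Table 3 in Section 8.2.1 sets green, amber and red limits for monthly recruitment and retention.

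**The concern.** A feasibility study is normally judged by the measures that show whether the next trial can be run. Here those measures sit outside the outcome list. The only outcome labelled primary is an effect score in a study that disclaims power.

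Two things are at stake. First, the report may be organised around a significance test, with recruitment and retention left as background. Second, the comparison of 60% with 100% is phrased as a question of equal effectiveness, while the planned test can only look for a difference. The 60% threshold is, in the protocol's account, the nationally accepted definition of completion, so a non-significant result could be taken as supporting it when the data cannot.

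**Working it through.** **Inputs.** 120 participants, four groups of 30 (Study Summary; Section 8.2.1). Alpha 5% (Section 6.4), taken as two-sided for pairwise comparisons because sidedness is not stated. Groups are taken as equal, as the protocol states, although Section 6.2 also mentions a 2:1 block strategy. Neither a DSMQ-R SD nor a target difference is given, so effects are in SD units of the change score: 0.5 SD because 6.4 uses it for the MCID, and 0.8 SD for comparison. Expected dropout is not stated; 24 per arm is 80% of 30 (the Table 3 green limit) and 18 per arm is 60% (its amber floor).

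**The plan's own figure.** 4 × 30 = 120. It is also consistent with the lower end of the 24–50 per group rule with 20% loss: 24 / 0.80 = 30. No power figure is stated, so there is none to reproduce.

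**Power of the planned ANOVA.** With group means spanning d SD, Cohen's f depends on where the middle groups lie:
- two groups at the extremes, two midway: f = d × √(1/8)
- evenly spaced: f = (d/2) × √(5/9)
- two groups at each end: f = d/2

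Power comes from the non-central F distribution with 3 and N − 4 degrees of freedom and non-centrality N × f². For d = 0.5 and N = 120, f = 0.177, 0.186 and 0.25, giving non-centrality 3.75, 4.17 and 7.5.

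| Range of means | Per arm | Two midway | Even | Two and two |
|---|---|---|---|---|
| 0.5 SD | 30 | 33% | 36% | 61% |
| 0.5 SD | 24 | 26% | 29% | 50% |
| 0.5 SD | 18 | 20% | 22% | 38% |
| 0.8 SD | 30 | 73% | 77% | 96% |

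The 18-per-arm row matters because 6.4 also removes anyone who did not complete the allocated amount, so the analysed number can fall below the number retained.

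**The two comparisons actually asked about.** 10% against none and 60% against 100% are pairwise, and 6.4 names no pairwise test. A two-sample t-test at 0.5 SD has 48% power with 30 per arm and 40% with 24.

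**Precision of a pairwise difference.** 95% half-width = t × √(2/n) SD.
- n = 30: 2.00 × 0.258 = 0.52 SD (0.51 with the error term pooled over four groups)
- n = 24: 2.01 × 0.289 = 0.58 SD (0.57 pooled)

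To lie inside ±0.5 SD, an interval can be at most 1.0 SD wide. These are at least 2 × 0.51 = 1.02 SD wide, so no observed difference would bring the 95% interval inside the MCID range, provided the same SD is used for both. A formal equivalence test uses the 90% interval: 1.67 × 0.258 = 0.43 SD at n = 30. That would need an observed difference within 0.5 − 0.43 = 0.07 SD, and no such test is planned.

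**Precision of a feasibility outcome at the same N.** Wilson 95% interval for retention of 96/120 = 80%: centre (0.80 + 3.84/240) / (1 + 3.84/120) = 0.791; half-width 1.96 × √(0.80 × 0.20/120 + 3.84/(4 × 120²)) / 1.032 = 0.071; interval 72.0% to 86.2%. No increase in N is needed to use it.

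**The case against.** The strongest reply is that the primary outcome is a deliberate choice that fits a stated aim. Most statements of aim concern patient-reported scores, Section 6.1 argues for these over HbA1c, and Section 8.2.1 justifies the sample size as adequate for estimating effect sizes. The abstract calls the scores preliminary, and the feasibility data will be collected and reported. All of that stands. A reader might infer that the primary outcome misses the study's purpose altogether, or that feasibility is not measured; the documents support neither. The gap is in outcome status, and it affects one of two stated purposes.

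Two further inferences go too far. One is that a non-significant result is likely: that depends on an effect size the documents do not give, and with a 0.8 SD range and 30 per arm the ANOVA has 73–96% power. The other is that the plan will read non-significance as equality. It nowhere says so, it also reports the MCID, and it treats significance as desirable rather than decisive. What remains is that the question is worded as equal effectiveness and nothing in 6.4 guards against that reading.

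Nor can Table 3 be taken as the rule for going on to a full trial. It is titled as progression criteria, but the text ties its recruitment targets to reaching an adequate sample for analysis, with shortfalls discussed with supervisors. It has no eligibility criterion, and exactly 13 recruits in a month falls between amber (14–16) and red (below 13).

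**Conclusion.** The point holds in this form: of two stated purposes, Section 5.2 gives outcome status to one, and the feasibility measures named elsewhere have none. The effect analysis is a 5% test in a study described as unpowered. For a 0.5 SD range of means its power is about 33–61% with 30 per arm and 26–50% with 24, depending on the pattern of means. With pairwise 95% half-widths of about 0.51–0.58 SD, a non-significant difference between 60% and 100% could not support equal effectiveness on the 0.5 SD scale.

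These figures assume equal groups, effects in SD units of change, and 24 per arm from the 80% retention limit. The sample size of 120 is not an arithmetic error and does not need to change.

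**What to change.** - **Section 5.2:** list recruitment, retention and eligibility rates as the primary (feasibility) outcomes, each with a 95% interval. Keep DSMQ-R change as the candidate primary outcome for the full trial, with PAID and PROMIS secondary.
- **Sections 4.1 and 6.4:** report between-group differences in score change, including 10% against none and 60% against 100%, as estimates with 95% intervals. Label p-values exploratory, and state that non-significance will not be read as equal effectiveness.
- **Sections 5.1 and 6.1:** bring the wording into line, with both purposes stated.
- **Table 3:** state that it informs the decision on a full trial, after assigning exactly 13 recruits per month to a category. Either add an eligibility criterion or say that eligibility is reported descriptively only.

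**Cost.** No new data and no change in N. The amendment touches 4.1, 5.1, 5.2, 6.1, 6.4 and Table 3. Under Section 10.5 the team must decide whether it is substantial, so it may need re-submission to the ethics committee. The thesis could no longer lead with an efficacy test.

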6.1 Design

This is a single-centre randomised feasibility study evaluating the impact of different completion rates of DSME programmes on psychometric outcomes specifically looking at ability to self-care, diabetes distress and quality of life. DSME will be the intervention and will typically be delivered within 3 weeks of the baseline appointment. There is a deliberate short separation between education intervention and follow up psychometric tests of 3-4 months to allow participants the opportunity to adopt any behaviour changes following the DSME programme whilst minimising the risk of not receiving the full NICE recommended DSME programme and to broadly align with landmark studies. Landmark studies namely DCCT (26,27) and DESMOND (25) evidenced a statistically

significant improvement to PROMs at 4 months post education intervention, however HbA_{1c} changes were not significant within this timeframe despite being statistically powered. A recent systematic review (38) concluded that as DSME is primarily focused on behavioural change to facilitate glycaemic control, efficacy measures should focus on behavioural and psychosocial changes, however these are often overlooked. This study is a feasibility trial and by its very nature is not statistically powered, therefore despite HbA_{1c} being arguably the measure of choice within the literature for measuring effectiveness of diabetes interventions, this study will use PROMs as its primary outcome measure.

6.2 Study processes

Screening and recruitment

Potentially eligible participants meeting the inclusion criteria and not excluded by exclusion criteria (outlined in section 8.1) who are either due to attend the diabetes centre for new patient clinic, have been referred for DSME intervention or are on the monthly shared care report for newly diagnosed type 2 diabetes requiring an offer of DSME will be screened for entry into the study and added to a screening log sheet (appendix 1). Potentially eligible participants due to attend new patient clinic will be invited into the study by NP clinic letter (appendix 1) with attached participant information sheet (PIS) (appendix 1). Letters will be posted ahead of their clinical appointment. For potential eligible participants identified through DSME referrals or the monthly shared care record report will be sent a telephone screening letter (Appendix 1) and PIS prior to meeting with the researcher. Study recruitment technique is outlined in further detail in section 8.2.2.

At the screening meeting potentially eligible participants will be asked to confirm they have read the PIS and invited to ask questions about the research. Where patients decline to take part in the research, they will be reassured this will not have any impact on their current or future treatment. Participants who give written informed consent will be enrolled onto the study. The researcher will utilise an informed consent checklist (Appendix 1) to ensure consistency and that all elements for informed consent have been completed. Participants will be consented for informing their GP, this is made clear in the PIS.

Visit 1

At enrolment baseline characteristics will be recorded from the electronic medical record, or where not available directly from the patient: NHS number, age, sex, ethnicity, diabetes duration, postcode, latest HbA_{1c}, prescribed glucose lowering agents, and a Charlson Comorbidity Index will be calculated. Postcode will be used to calculate indices of multiple deprivation (IMD) score.

Participants (n=120) will be randomised by permuted block strategy of 2:1 across four groups using an online randomisation software application designed for clinical trials (51,52). Due to the design of this study randomisation will not be blind to the researcher or participants. Group design will be as follows:

- Group 1: DSME 6 hours, 100% completed (completed).
- Group 2: DSME 3 hours 36 minutes, 60% completion (partial completion)

- Group 3: DSME 36 minutes, 10% of content (attended)
- Group 4: Delayed education (education not offered, not attended, or declined)

DSME programme overview is provided in appendix 1 giving a broad overview of DSME content by programme completion status. Local demographic data suggests that of the local population 46.4% are living in the most deprived neighbourhoods within the UK (9). Of the local population 19.3% have a reading age of 9-11 or below (53,54), are classed as being functionally illiterate and are therefore likely to struggle reading a paper questionnaire. Verbal support for completing the PROMs will be offered by the researcher to ensure participants from lower socioeconomic backgrounds are not excluded from participating in the DIABETES PRO study as they are evidenced to make up a larger proportion of people with diabetes (55-57). Support will be limited to reading the questions verbatim.

Participants will be asked to complete three psychometric tests measuring self-care activities, diabetes distress and quality of life using the following validated tools: Diabetes Self-Management Questionnaire-Revised (DSMQ-R)(48), Problem Areas in Diabetes (PAID) scale (49) and the Patient Reported Outcome Measures Information System (PROMIS) Global Health scale v1.2 (50) (appendix 1).

Participants in groups 1, 2 and 3 will be asked to book a DSME session with the researcher, typically this should be no longer than 3 weeks from study enrolment. Research group DSME programmes (intervention) will be run by the researcher separate to routine patient DSME to minimise disruption of participants leaving part way through on patients.

Participants randomised to group 4, delayed education will not be required to attend DSME as part of the DIABETES PRO study. Collected data will be collected and managed using Research Electronic Data Capture (REDCap) electronic data capture tools. A REDCap data collection tool has been included in Appendix 1 for reference. REDCap is a secure, web-based software platform designed to support data capture for research studies, providing an intuitive interface for validated data capture; audit trails for tracking data manipulation and export procedures; automated export procedures for seamless data downloads to common statistical packages; and procedures for data integration and interoperability with external sources (58,59) (see section 3.6 for further details).

Visit 2

To ensure there is enough information about the intervention within this study particular consideration has been given to discussing areas the National Institute for Health Research (NIHR) report to be inadequately detailed in rejected health research proposals (60). See table 2.

Table 2: NIHR adapted final checklist for health research proposals. (60)

Organisation	Mersey and West Lancashire Teaching Hospitals NHS Trust, previously St Helens and Knowsley Teaching Hospitals NHS Trust
• What type of trust is involved?	

DIABETES-PRO study	Study Protocol	Version 1.1.0	Date 27.03.24
		IRAS ID337691	

 • How big is the organisation? • How many study sites? 	
and Southport and Ormskirk NHS Trust serves a population of over 600,000 delivering care across 5 hospital sites, intermediate care, primary care, and community-based services.
 
The specialist diabetes centre is based at St Helens Hospital and will be the single study centre for this research.

Location 
 • What type of area is it? • Population demographics 	
The borough of St Helens has a legacy of poor health linked with deprivation and the town's industrial past. St Helens is ranked as the 26th most deprived local authority in England, its relative position having deteriorated since 2015 with almost 25% of residents living in the 10% most deprived neighbourhoods in the country (34).
 
St Helens has widespread health deprivation with a higher-than-average diabetes prevalence of 9.2% (14,935 individuals) (20), versus 7.3% in England (35).

Patient group 
 • Who is receiving the intervention? • How many patients are being seen? • Characteristics of the patients? 	
Patients with type 2 diabetes referred to the Diabetes Centre, St Helens Hospital for specialist intervention and / or DSME and / or registered with a St Helens GP and opted into data sharing will be screened for entry.
 
The Diabetes department works closely with primary care colleagues to offer specialist advice, education, and guidance to patients with diabetes who are assessed and then discharged for clinical management by their GP. Referrals for DSME are made directly from primary care into DSME education sessions. The shared care report highlights any patient with a local GP who has had a first use of a type 2 diabetes code within the last month and have opted into data sharing. The use of the three recruitment streams for this study allows for a sample which is representative of the local population and is not limited to only patients requiring specialist led care.
 
The DIABETES PRO study will aim to recruit 120 participants which will be randomised across four groups containing 30 participants each.
 
Patients ≥18 years of age from a variety of socioeconomic backgrounds. St Helens has a predominantly white British population (96.5%), and this is likely to be represented in the sample (37).

Workforce and staffing 
 • Staffing skill, grade and 	
The researcher is employed by the Diabetes Centre as a clinical research fellow and is a Fellow of the HEA with experience teaching

profession • Staff new or existing • Training needed to deploy the intervention?	adult learners within higher education settings. The researcher has a clinical background as a podiatrist and is currently registered with the HCPC. The researcher is the patient education lead within the department and is in the process of accrediting the DSME programme with QISMET.
Intervention • How is the intervention different from normal care? • What does it look like? • Is it clear when it starts and finishes?	Clinical intervention of participants will not be altered. Participants will receive the same DSME programme as routine clinical patients. Normal delivery of DSME programmes is by a diabetes specialist nurse or dietitian. Research DSME programmes will be, where possible, delivered by the researcher for consistency. Participants will be reminded at the beginning of the DSME programme that this is a research study and that some participants will leave after 36 minutes, 3 hours and 36 minutes, with others remaining for the full 6 hours programme. Reminders will be given at the time points in which participants from groups 2 and 3 should leave.
Contextual information • Policy initiatives related to the intervention?	DSME is NICE recommended for all patients newly diagnosed with type 2 diabetes with annual refresher thereafter (15). The National Diabetes Audit suggests 71% of people with type 2 diabetes are offered DSME, with an average attendance rate of 7%. Local records suggest that of those that start DSME (9%) only 12.6% complete the programme (20).

Visit 3

Between 3-4 months post intervention participants will be asked to repeat baseline psychometric tests. For participants in group 4 this will be 4 months from enrolment. This will be the end of the study.

At the end of the study participants in groups 2, 3 and 4 will be offered a full DSME programme.

